4.3 Intervention

Intervention Group:

The following sections of the discharge letter are automatically converted into a plain-language version by the locally implemented LLM system (GPT-OSS, on-premise): Current Status, Medical History, Epicrisis, and Further Management. A study physician reviews the LLM-generated synopsis for content accuracy and makes corrections as necessary. The patient receives the simplified version in addition to the standard synopsis.

Control Group:

The patient receives the standard synopsis only.

Translation Arm:

The specified sections of the discharge letter (Current Status, Medical History, Epicrisis, Further Management) are simplified by the LLM system and translated into the patient's native language. The translation is reviewed by a native-speaker reviewer.

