Statistical Analyses	t-test / Mann-Whitney U-test for primary endpoint; chi-squared / Fisher for categorical endpoints; multivariate regression adjusted for educational level and further covariates; ITT analysis. Analysis with R or SPSS.
Study Duration	12 months recruitment (April 2026 – March 2027), data analysis complete June 2027

2 Rationale

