3.1 Primary Objective

To evaluate the superiority of LLM-generated, simplified patient synopses over standard synopses with respect to patient comprehension in hematology and oncology.

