3.3 Endpoints

Primary Endpoint:

Comprehension score of the patient synopsis, measured using a 5-item scale (10-point Likert, based on PEMAT). The score is calculated as the mean of five items: overall comprehension, comprehension of the diagnosis, the treatment, the next steps, and medical terminology.

Secondary Endpoints:

- Patient satisfaction (EORTC QLQ-INFO25 subscales)
- Subjective uncertainty reduction (single item, 0–10 scale, measured before and after reading the synopsis)
- Preference for synopsis format (categorical variable)
- Health literacy as a covariate (HLS-EU-Q6)
- Time for physician review (in minutes) and correction rate
- Translation quality (rated by native-speaker reviewers, 5-point scale)

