3.4 Hypotheses

H1: LLM-simplified patient synopses achieve a significantly higher comprehension score (difference of at least 1.5 points on the 10-point scale) compared to standard synopses.

H0: There is no difference or a difference of less than 1.5 points between the groups.

4 Study Procedures

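### The objective and H1 claim that simplified synopses beat standard ones, but the arms compare standard plus simplified with standard alone, and the text being scored is not fixed to be the same in both arms

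*Protocol*

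**What the plan says.** Section 3.1 gives the primary objective as "To evaluate the superiority of LLM-generated, simplified patient synopses over standard synopses with respect to patient comprehension in hematology and oncology"; the synopsis table in Section 1 has the same aim. Section 3.4 puts it as a hypothesis about the two kinds of text: "LLM-simplified patient synopses achieve a significantly higher comprehension score (difference of at least 1.5 points on the 10-point scale) compared to standard synopses". H0 is the complement, expressed as a difference between the groups.

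Section 4.3 defines the groups. Intervention: "The patient receives the simplified version in addition to the standard synopsis". Control: "The patient receives the standard synopsis only". The synopsis table describes the arms in the same way, and Section 4.1 gives the additional, visibly different text as the reason why blinding is not possible.

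Section 3.3 defines the primary endpoint as "Comprehension score of the patient synopsis, measured using a 5-item scale", the mean of five items covering overall understanding, diagnosis, treatment, next steps and terminology. Section 4.2 allows for one or several synopses being handed out, with the same minimum reading time of 15 minutes. A single questionnaire follows on Day 0, and there are no later visits.

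**The concern.** The objective and H1 contrast one kind of text with another. The arms contrast two texts with one. No randomised arm receives the simplified text alone, so the comparison named in 3.1 and 3.4 is not one that randomisation delivers. If the result is positive and is reported in the words of the objective, the report will claim more than the design shows.

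The endpoint adds to this. It refers to one synopsis, but intervention patients have two in hand. Unless the questionnaire says which text is meant, the two arms may be answering different questions, and an analysis plan written later cannot recover what a patient had in mind on Day 0.

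**Working it through.** **Step 1: what randomisation identifies.** Write S for the mean score with the standard text alone, B for the mean with both texts, and L for the mean with the simplified text alone.

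- Contrast claimed (3.1 and H1, read literally): L − S.
- Contrast delivered (4.3): B − S.
- Identity: B − S = (L − S) + (B − L).

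L is observed in no randomised arm, so B − L cannot be estimated. It contains whatever follows from having a second text on the same content. Its sign is unknown: repetition could raise the score, and more material could lower it. The translation arm does not help, because it is non-randomised, enrols a different population and adds translation.

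The score comes from Likert items that the patient completes knowing which material was received. The blinded questionnaire evaluation in Section 4.1 does not blind the respondent. B − S is thus an effect on self-rated comprehension in an open-label setting.

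**Step 2: which text is scored.** Section 3.3 leaves three readings open for an intervention patient:

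| Text rated in the intervention arm | What the between-arm difference then means |
|---|---|
| Simplified text | A score of one text against a score of another, but from patients who also hold the standard text |
| Standard text | Whether having the simplified text helps patients follow the standard one |
| Everything received | The effect of the add-on strategy on understanding of the written information |

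Only the third reading puts the same question to both arms and matches the design.

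**Step 3: does the sample size depend on the contrast?** Inputs from Section 9: difference 1.5, SD 2.5, two-sided 5%, power 80%, ratio 2:1. The normal approximation for the control arm is (1.960 + 0.842)² × 2.5² × (1 + 1/2) / 1.5² = 7.85 × 6.25 × 1.5 / 2.25 = 32.7. That rounds up to 33 controls and 66 intervention, 99 in all; the exact t calculation gives 34 + 68 = 102. The stated 136 (91 and 45) is not reproduced and corresponds to about 90% power, but that is a separate matter. Nothing in the formula refers to which contrast the 1.5 points describe, so the mismatch does not alter the number of patients.

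**Step 4: format preference, as a side point.** Controls see one format. With 100 intervention patients less 10% dropout, 100 × 0.9 = 90 remain. The 95% half-width for the share choosing any one category is 1.96 × √(p(1 − p)/90): 0.103 at p = 0.5, 0.095 at p = 0.7 and 0.083 at p = 0.8. A summary within the intervention arm is therefore feasible, at about 8 to 10 percentage points either way. The values of p are assumptions.

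**The case against.** The strongest reply is that the add-on design is legitimate and fully disclosed. The synopsis table and Sections 4.1, 4.3 and 8 all describe an additional text. The discharge letter is routine care, so adding to it is the choice a clinic would actually face. Randomisation estimates that effect validly. All of this stands, and no new arm is asked for. Disclosing the design in one place does not, however, correct the claim in another.

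A second reply is that the questionnaire is not in the protocol and its stem may name the text. Diagnosis, treatment and next steps can also be rated as content, whether a patient holds one text or two. This stands in part: it is not shown that patients will in fact rate different things. But overall understanding and terminology, two of the five items, depend more on the text in view, and the protocol's own definition of the endpoint leaves the text open.

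A reader might go further and infer that format preference and correction rate will be tested between arms, because the synopsis names "chi-squared / Fisher for categorical endpoints". The protocol does not support that. It nowhere says that either is compared between groups. A chi-squared test can equally be used within one arm, an analysis plan not at hand may restrict the population, and Section 3.2 speaks only of documenting the correction rate. Nor is a test of preference against 50% warranted, because the levels of the variable are not defined and there may be more than two. No error is claimed on these points.

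**Conclusion.** The mismatch is real and can be read directly from Sections 3.1, 3.4 and 4.3. A positive result would show that giving a reviewed simplified text on top of the standard one raises self-rated comprehension. It would not show that the simplified text is better than the standard one. The lack of a fixed rated text in 3.3 is a second, smaller defect in the same definition.

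On size: the effect is on the meaning of the primary result, not on its test, precision or sample size. It cannot be put in points on the scale, because B − L is not estimable from this design.

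It would be too strong to infer that the randomised comparison is invalid or that the design must change; the documents describe a sound add-on trial. The conclusion assumes that H1 is meant as worded, and that the questionnaire, which is not shown, does not already define the text to be rated. If it does, only the rewording of the objective and hypotheses, and a matching line in 3.3, remain. The change should be made before recruitment starts, planned for April 2026.

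**What to change.** - In the synopsis objective, 3.1 and 3.4, state the contrast as *standard plus LLM-simplified synopsis versus standard synopsis alone, on self-rated comprehension*.
- In 3.3 and in the questionnaire stem, state that patients in both arms rate the five items for all the written information they received.
- If format preference is analysed, summarise it in the intervention arm only, as proportions with 95% confidence intervals. This is a clarification, not the correction of an error.

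The cost is a wording change to the protocol and the questionnaire. The arms, visits and sample size stay as they are. The downside is a narrower headline claim: the trial will speak to adding a simplified text, not to replacing the standard one.

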oncOPAL — Oncology Optimized Patient-Accessible Language

Study Protocol

Prospective Randomized Controlled Trial to Evaluate Locally Implemented Large Language Models (LLMs) for Simplifying Patient Communication in Hematology and Oncology

Date: 18.03.2026

Version: 1.0

Study Code: oncOPAL

Principal Investigators

Dr. med. [name]

PD Dr. med. [name]

TUM University Hospital (Klinikum rechts der Isar)

[name]

1 Protocol Synopsis

Short Title	oncOPAL
Title	Prospective Randomized Controlled Trial to Evaluate Locally Implemented Large Language Models (LLMs) for Simplifying Patient Communication in Hematology and Oncology
Study Center	TUM University Hospital (Klinikum rechts der Isar)
Study Design	Prospective, randomized controlled trial with parallel group design. Block randomization 2:1 (intervention : control) with permuted blocks of variable size (4–6). Additionally, a non-randomized translation arm for non-German-speaking patients.
Study Population	Inpatients of the Department of Medicine III (Hematology/Oncology) at TUM University Hospital who receive a discharge letter including the sections Current Status, Medical History, Epicrisis, and Further Management as part of routine clinical care.
Rationale	Up to 40–80% of medical information is not correctly recalled or understood by patients. LLMs can convert medical texts into plain-language versions with high accuracy. However, prospective RCTs evaluating the clinical benefit of LLM-simplified patient synopses are lacking.
Primary Objective	To evaluate the superiority of LLM-generated, simplified patient synopses over standard synopses with respect to patient comprehension.
Intervention	Intervention group: The following sections of the discharge letter are simplified by the LLM system: Current Status, Medical History, Epicrisis, and Further Management. The patient receives the LLM-

	simplified version in addition to the standard synopsis (after physician review). Control group: Standard synopsis only. Translation arm: LLM-simplified and translated synopsis of the same sections.
Sample Size	180 patients (150 randomized: 100 intervention, 50 control; 30 translation arm)
Primary Endpoint	Comprehension score (5-item scale, 10-point Likert, based on PEMAT)
Secondary Endpoints	Patient satisfaction (EORTC QLQ-INFO25 subscales), uncertainty reduction, format preference, physician review workload, correction rate, translation quality

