4.2 Study Procedures

Potential participants are identified during inpatient stays in the Department of Medicine III. Following verification of inclusion and exclusion criteria, informed consent is obtained in writing (with a reflection period of at least 24 hours). Randomization or assignment to the translation arm then follows.

Day 0 (as part of the regular hospital visit):

- Informed consent procedure (approx. 10–15 minutes)
- Randomization or assignment to the translation arm
- Preparation of the synopsis as part of routine clinical care
- LLM simplification and physician review where applicable
- Distribution of synopsis/synopses with at least 15 minutes reading time
- Completion of the questionnaire (approx. 5–10 minutes)

No further study visits are planned. Study participation is complete upon submission of the questionnaire.

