6.1 Inclusion Criteria

- Age 18 years or older
- Inpatients of the Department of Medicine III (Hematology/Oncology) at TUM University Hospital
- Receipt of a discharge letter including the sections Current Status, Medical History, Epicrisis, and Further Management as part of routine clinical care
- Capacity to provide informed consent
- Written informed consent following the consent procedure

Additional Inclusion Criteria for the Translation Arm:

- Insufficient German language proficiency
- Native language supported by the LLM system (English, Turkish, Arabic, Russian, Polish, Spanish, Italian, French, Portuguese, Vietnamese, Chinese)

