7.7 Access Control

Access to study data is protected by individual user accounts with strong passwords and is logged. Servers are located in a secured data center with access control.

8 Benefit-Risk Assessment

The benefit-risk ratio is favorable. Participants in the intervention group and translation arm receive an additional plain-language synopsis that can promote understanding of diagnosis and treatment. Study participation involves minimal burden (additional time requirement of approximately 5–15 minutes). There are no physical risks. Psychological risks are low; the risk of possible misunderstandings arising from the simplified presentation is mitigated by mandatory physician review. Routine clinical care remains completely unchanged.

9 Sample Size and Power Analysis

The sample size calculation is based on the following assumptions: a clinically relevant difference in the primary endpoint of 1.5 points, an expected standard deviation of 2.5 points, power of 80%, significance level $\alpha = 0.05$ (two-sided), a randomization ratio of 2:1, and an expected dropout rate of 10%.

For a two-sided t-test for independent samples, the required sample size is $n = 136$ (91 intervention, 45 control). Accounting for the dropout rate, $n = 150$ patients will be recruited for the randomized part.

For the translation arm, $n = 30$ patients will be enrolled. This sample size permits a descriptive evaluation of feasibility without a formal statistical comparison.

10 Funding

The study is funded through internal resources of the Institute for Diagnostic and Interventional Radiology and the Department of Medicine III at TUM University Hospital (Klinikum rechts der Isar). There are no conflicts of interest.

11 References

1. Kessels RPC. Patients' memory for medical information. J R Soc Med. 2003;96(5):219-222.
2. Jeblick K, et al. ChatGPT Makes Medicine Easy to Swallow: An Exploratory Case Study on Simplified Radiology Reports. Radiology. 2024;308(1):e230618.

3. Ayers JW, et al. Comparing Physician and Artificial Intelligence Chatbot Responses to Patient Questions Posted to a Public Social Media Forum. *JAMA Intern Med.* 2023;183(6):589-596.
4. Arraras JL, et al. The EORTC QLQ-INFO25: A questionnaire to assess information given to cancer patients. *Eur J Cancer.* 2010;46(15):2726-2738.
5. Basch E, et al. Overall Survival Results of a Trial Assessing Patient-Reported Outcomes for Symptom Monitoring During Routine Cancer Treatment. *JAMA.* 2017;318(2):197-198.

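### Section 8 relies on mandatory physician review for all simplified text, but section 4.3 and the synopsis prescribe it only for the intervention group, not the translation arm

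*Protocol*

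**What the plan says.** Section 8 (Benefit-Risk Assessment) identifies who gets simplified text: "Participants in the intervention group and translation arm receive an additional plain-language synopsis". Later in the same paragraph it states the safeguard: "the risk of possible misunderstandings arising from the simplified presentation is mitigated by mandatory physician review". That sentence limits the safeguard to neither arm.

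Section 4.3 (Intervention) sets out the procedure arm by arm. Under the intervention group: "A study physician reviews the LLM-generated synopsis for content accuracy and makes corrections as necessary". Under the translation arm, the same four sections of the discharge letter are simplified by the LLM and put into the patient's native language, and the only check named is "The translation is reviewed by a native-speaker reviewer".

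The synopsis follows the same pattern. The intervention group receives the "simplified version in addition to the standard synopsis (after physician review"), whereas the other entry reads "Translation arm: LLM-simplified and translated synopsis of the same sections", with no review mentioned.

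The day 0 list in section 4.2 has one line on the matter, "LLM simplification and physician review where applicable", and names no arm.

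**The concern.** The benefit-risk assessment relies on a safeguard that the procedural text does not prescribe for one of the two arms exposed to the risk. If staff follow section 4.3 as written, translation-arm patients can be handed machine-simplified and machine-translated text about their status, history and further management without any physician having been required to check its content.

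The native-speaker review is a real check, but its stated object is the translation. A faithful translation of a wrong simplification could pass it. The text in this arm goes through two LLM steps, simplification and translation, where the intervention group's text goes through one, yet its prescribed content check is the weaker of the two. Patients enter this arm because their German is insufficient (section 6.1), so they are poorly placed to spot an error by reading the German letter alongside.

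**Working it through.** This is a question of consistency between sections. It depends on no effect size, variance, alpha or power, and the protocol gives no figure to reproduce. The check is to set every mention of review side by side and ask which arm it covers.

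| Place in the protocol | Intervention group | Translation arm |
|---|---|---|
| Section 8, recipients of simplified text | named | named |
| Section 8, physician review as safeguard | covered, no exception | covered, no exception |
| Section 4.3, physician check of content | prescribed | not prescribed |
| Section 4.3, native-speaker check of the translation | not relevant | prescribed |
| Synopsis, review before handing over | by a physician | none stated |
| Section 4.2, day 0 line | arm not named | arm not named |
| Sections 3.2 and 3.3, review time and correction rate | arm not named | arm not named |

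The two arm-specific descriptions, section 4.3 and the synopsis, agree with each other: physician review belongs to the intervention group. The remaining operational mentions are general and assign review to no particular arm. Only section 8 extends physician review to both arms, and it is a risk statement that sets no procedure.

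Next, could the native-speaker reviewer supply the physician check? Sections 3.2 and 3.3 describe these reviewers as assessing translation quality, on a 5-point scale. Nowhere are they said to be physicians, to compare the text with the discharge letter, or to correct it. The protocol does not establish that they fill that role.

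The size follows from the planned numbers in the synopsis:

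- Patients receiving LLM text: 100 (intervention) + 30 (translation) = 130.
- Share with no physician check prescribed in section 4.3: 30 / 130 = 23.1%.
- Physician reads if the check is extended: 100 + 30 = 130, an increase of 30 / 100 = 30%.
- Native languages allowed in section 6.1: 11, so a study physician cannot be assumed able to read the translated texts.

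**The case against.** The best defence is that the protocol already states the requirement. Section 8 calls physician review mandatory in a paragraph that covers both arms. The translation-arm text in section 4.3 excludes nothing and can be read as adding a further, arm-specific step. Sections 3.2 and 3.3 refer to physician review of LLM synopses without restricting it. In section 4.2 the qualifier may serve only to exclude controls, who get no LLM text; if it governs simplification and review together, review goes wherever simplification goes. On this reading section 4.3 is merely incomplete.

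That reading is possible, and the investigators may intend it. But it has to be inferred: none of these places names the translation arm, and a general reference to review cannot make it compulsory there when the two arm-specific descriptions mention it only for the other group. If section 8 is instead read as meaning the intervention group alone, the translation arm is left with no stated safeguard for this risk. Either way the text needs correcting.

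Several limits do stand. The translation arm is not unreviewed, since a native speaker checks the translation. The 23% is a headcount; the protocol gives no error rate from which to estimate harm. Section 8 rates the psychological risks as low. The arm is non-randomized and descriptive, so the primary endpoint, the randomized comparison and the sample size are untouched.

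**Conclusion.** The concern holds. The safeguard claimed in section 8 is not backed by the procedure for the translation arm: 30 of the 130 planned recipients of LLM text (23%) have no physician content check prescribed. This rests on reading section 4.3 as the operative procedure and on the planned arm sizes. It does not assume that such checks would be omitted in practice, only that the protocol does not require them. It is a patient-safety and consistency defect that should be corrected before enrolment into that arm; it does not threaten the trial's inference.

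**What to change.** In section 4.3 and the synopsis, state that a study physician also checks the translation arm's simplified content against the discharge letter before it is handed over, in addition to the native-speaker check, and that review time and corrections are recorded as in the intervention group. The languages allowed are wide-ranging ("Native language supported by the LLM system (English, Turkish, Arabic, Russian, Polish, Spanish, Italian, French, Portuguese, Vietnamese, Chinese"), so the physician should check a German simplified version, and the corrected version should then be translated. In section 4.2, replace the open qualifier with the names of the arms.

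The cost is wording in three places plus about 30 further physician reads. The protocol does not say whether the system simplifies and translates in one step; if it does, one added step is needed to produce the German intermediate text.

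If physician review of this arm is not intended, restrict the section 8 safeguard to the intervention group and assess the translation arm's risk, and what the native-speaker check does and does not cover, in a separate statement. That costs wording only.
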